11.2. Justification of Sample Size

Since this is an open-label single treatment arm study, formal statistical testing is not planned. Therefore, a calculation for patient sample size is not applicable.

Six patients are planned to be enrolled for Part A and 14 pediatric patients are planned to be enrolled for Part B, considering the recruitment constraints in this rare patient population.

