11.4.3.2. Secondary Efficacy Analysis for Part B

For the secondary efficacy endpoints (defined in Section 4.1.2), descriptive summaries and analyses will be performed in the ITT population, using values obtained regardless of adherence to study treatment and subsequent therapies (ITT estimand).

For descriptive summaries, percent change, and when appropriate change from baseline, in calculated LDL-C, total-C, non-HDL-C, Apo B, and Lp(a) will be provided at each time point during the 24-week open-label treatment period. All measurements, scheduled or unscheduled, will be assigned to analysis windows defined in the SAP in order to provide an assessment for these time points. Laboratory assessments other than the ones provided by the central laboratory will be excluded. The time profile of each parameter will be plotted with the corresponding SEs.

Multiple types of measurements are planned to be analyzed during differing time points in the trial, specifically continuous measurements expected to have a normal distribution (eg, percent change in calculated LDL-C), continuous measurements expected to have a non-normal distribution [eg, Lp(a)], and binary measurements (eg, proportion of patients with $\geq 50\%$ reduction in calculated LDL-C).

I Continuous endpoints anticipated to have a normal distribution

Continuous secondary efficacy endpoints anticipated to have a normal distribution (ie, lipids other than Lp(a)) will be analyzed using the same PMM approach as for the primary endpoint. In addition, the same sensitivity analyses using MMRM approach as for the primary endpoint will be conducted in the ITT population and mITT population.

II Continuous endpoints anticipated to have a non-normal distribution

Continuous secondary efficacy endpoints anticipated to have a non-normal distribution (ie, Lp(a)), will be analyzed using a robust regression model (ie, ROBUSTREG SAS procedure with M-estimation option) with baseline value as a covariate. Missing values will be addressed using a multiple imputation approach, which will be described in the SAP. The combined means will be provided with respective SE estimates and 95% CI.

III Binary Endpoints

Binary secondary efficacy endpoints will be analyzed with multiple imputation approach for handling of missing values, which will be described in the SAP. Combined proportions will be provided with corresponding 95% CI.

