2.2. Sample Size and Power Considerations

Since this is an open-label single treatment arm study, formal statistical testing is not planned. Therefore, a calculation for patient sample size is not applicable.

[figure not shown]
Six patients are planned to be enrolled for Part A and 18 pediatric patients are planned to be enrolled for Part B, considering the recruitment constraints in this rare patient population.

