4.7.1. Primary Efficacy Variable (s)

The primary efficacy endpoint for Part B is:

- The percent change in calculated LDL-C from baseline to week 24 (intent-to-treat [ITT] estimand) in Part B. The primary endpoint is defined as: $100 \times (\text{calculated LDL C value at week 24} - \text{calculated LDL-C value at baseline}) / \text{calculated LDL-C value at baseline}$.

The baseline LDL-C value is defined as the last calculated LDL-C value obtained before the first dose of study treatment in Part B. The calculated LDL-C at week 24 will be the LDL-C value obtained within the week 24 analysis window.

The intent-to-treat estimand used for the primary efficacy analysis is the treatment policy strategy, specifically the occurrence of the intercurrent events is irrelevant; the value for the primary efficacy endpoint is used regardless of whether or not the intercurrent events occur. The intent-to-treat estimand for the primary efficacy analysis is defined as:

- A. The patient population is defined as the Intent-to-treat population (Section 3.1.1).
- B. The primary efficacy endpoint is defined above.
- C. The intercurrent events of interest are the administration of study treatment and the administration of subsequent therapies. The interruption of study treatment and the change in subsequent therapies are ignored, and the value for the primary efficacy endpoint is used regardless of adherence to study treatment and subsequent therapies.
- D. The population-level summary for the primary efficacy endpoint is evinacumab mean value, SE and 95% confidence interval.

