5.7.1.1. Sensitivity of the Primary Efficacy Analysis

Robustness of the primary analysis statistical method will be assessed through sensitivity analyses, including an ITT analysis and an on-treatment analysis of the percent change in calculated LDL-C from baseline to week 24 using a mixed-effect model with repeated measures (MMRM) approach.

Sensitivity to Non-Good Clinical Practice (GCP) Compliant Sites

To assess the impact of non-GCP compliance sites on the primary efficacy endpoint, the primary efficacy analysis will be performed excluding non-GCP compliant sites. Sites known to be non-GCP compliant at the time of database lock will be identified for this analysis before database lock. Any additional sites determined to be non-GCP compliant post-database lock will be separately identified.

Sensitivity to the Handling of Missing Data

Sensitivity analyses will be conducted to assess the robustness of the primary efficacy analysis with regards to the handling of missing data ([Little RJ 2012](#)).

Mixed-effect Model with Repeated Measures (MMRM) Approach

The percent change from baseline in calculated LDL-C at week 24 will be analyzed in the ITT population using a mixed effect model with repeated measures (MMRM) approach. All post-baseline data available within week 1 to week 24 analysis windows regardless of adherence to treatment and subsequent therapies will be used and missing data are accounted for by the MMRM model. The MMRM model assumes “missing-at-random” (MAR). The model will include the fixed categorical effect of time point (weeks 1, 2, 4, 8, 12, 16, 20, and 24), as well as the continuous fixed covariates of baseline calculated LDL-C value.

This model will be run using Statistical Analysis Software (SAS) mixed procedure with an unstructured correlation matrix to model the within-patient errors. Parameters will be estimated using restricted maximum likelihood method with the Newton-Raphson algorithm. Denominator degrees of freedom will be estimated using Satterthwaite’s approximation. This model will provide baseline adjusted least-squares mean estimate at week 24 with their corresponding standard error.

Sensitivity to On-treatment Calculated LDL-C Values

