5.7.2.2. Continuous Endpoints Anticipated to have a Non-Normal Distribution

Continuous secondary efficacy variables defined in Section 4.7.2 anticipated to have a non-normal distribution (i.e. Lp(a)) will be analyzed using the multiple imputation approach for handling of missing values as described in Appendix 10.5, with data log-transformed before imputation process and then back transformed to create the imputed data sets using the TRANSFORM statement of SAS MI procedure.

The percent change from baseline at time point of interest will be derived from observed and imputed lipid values at this time point. Multiple imputation will be followed by robust regression model (Mehrotra, 2012), with the endpoint of interest as the response variable using M-estimation (using SAS ROBUSTREG procedure) with corresponding baseline value(s). Combined means estimates with their corresponding SEs and 95% CIs will be provided through the SAS MIANALYZE procedure.

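### In single-arm Part B, the Lp(a) standard error and 95% CI taken at the mean baseline are conditional on the observed baselines, and the SAP does not say at which baseline the mean is evaluated

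*SAP*

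**What the plan says.** Lp(a) percent change is the one secondary endpoint treated as non-normal. Protocol 11.4.3.2 (II) specifies a robust regression, described as "ie, ROBUSTREG SAS procedure with M-estimation option) with baseline value as a covariate". SAP 5.7.2.2 repeats this after multiple imputation and adds: "Combined means estimates with their corresponding SEs and 95% CIs will be provided through the SAS MIANALYZE procedure". Neither text says that baseline is centred, or at which baseline value the mean is to be taken.

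The target comes from the estimand. Definition D in SAP 4.7.1 sets the population-level summary as "evinacumab mean value, SE and 95% confidence interval", and SAP 4.7.2 applies it to the continuous secondary endpoints, Lp(a) included.

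The MMRM sensitivity analyses of the primary endpoint (SAP 5.7.1.1, Protocol 11.4.3.1) also carry baseline LDL-C as a fixed covariate. SAP 5.7.1.1 says: "This model will provide baseline adjusted least-squares mean estimate at week 24 with their corresponding standard error". No CI is stated for them. The primary analysis (SAP 5.7.1) takes a plain mean with PROC MEANS and has no covariate.

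**The concern.** In a randomised trial, a baseline covariate removes noise from a difference between arms. Part B has no second arm. The fitted value at the average baseline is then essentially the raw mean, but the model SE treats the observed baselines as fixed and reports only the scatter around the regression line. A new sample of children would have a different average baseline. If percent change depends on baseline, that adds variability which the SE leaves out.

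The 95% CI from SAP 5.7.2.2 is the only interval planned for Lp(a). No hypothesis is tested, so readers will rely on estimates and their stated precision. For the MMRM, the stake is comparability: its SE can look smaller than the primary SE merely because it conditions on baseline.

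Separately, a regression with an intercept and a slope has no single mean until an evaluation point is named. Two programmers could follow the SAP and report different numbers.

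**Working it through.** **Inputs.** Protocol 11.2: "Six patients are planned to be enrolled for Part A and 14 pediatric patients are planned to be enrolled for Part B". SAP 2.2, written to Amendment 1, still has "Six patients are planned to be enrolled for Part A and 18 pediatric patients are planned to be enrolled for Part B". I use n = 14. The plan gives no SD, SE or correlation, and on sample size says "a calculation for patient sample size is not applicable", so there is no figure to reproduce. R² is my assumption, ranged from 0 to 0.3.

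**Step 1: SE at the mean baseline, complete data, least squares.** Let y = a + b·x + e in one arm.
- Fitted value at x̄: the raw mean ȳ.
- Model SE: s_res/√n.
- Sampling variance over new patients: σ_res²/n + b²·Var(x)/n = Var(y)/n.
- Since σ_res² = (1 − R²)·Var(y), model SE over true SE = sqrt(1 − R²).

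With normal data, coverage of the model's t interval for the population mean is P(|t₁₂| ≤ 2.179·sqrt(1 − R²)).

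| R² | Factor | Model SE (SD units; true 1/√14 = 0.267) | Too small by | Adjusted limit for t₁₂ | Coverage |
|---|---|---|---|---|---|
| 0 | 1.000 | 0.267 | 0% | 2.179 | 95.0% |
| 0.1 | 0.949 | 0.254 | 5% | 2.067 | 93.9% |
| 0.2 | 0.894 | 0.239 | 11% | 1.949 | 92.5% |
| 0.3 | 0.837 | 0.224 | 16% | 1.823 | 90.7% |

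At n = 18, coverage is lower by 0.2 points or less.

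Within one dataset, the ratio of the adjusted SE to SD/√n is sqrt((1 − r²)(n − 1)/(n − 2)) with the sample r². At n = 14 it is 1.04 at r² = 0 and 0.87 at r² = 0.3. The adjusted SE is the smaller one only when r² exceeds 1/13 = 0.077.

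**Step 2: closer to the planned methods.** These are simulations with 3,000 runs, n = 14, complete data, and correlation r = 0, 0.3, 0.5 (R² = 0, 0.09, 0.25).
- M-estimation at the mean baseline (lognormal baseline, CV 0.8): coverage 94.3%, 92.6%, 90.0% with a t quantile, and 92.3%, 90.3%, 87.4% with a normal quantile. The shortfall at r = 0 is a small-sample effect, not conditioning.
- Unstructured MMRM with four visits: model SE over empirical SE is 0.97, 0.90, 0.83. The 0.97 at r = 0 is again a small-sample effect.

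**Step 3: if an uncentred intercept were reported.** It is the prediction at Lp(a) = 0. Its SE relative to that at the mean baseline is sqrt(1 + n/((n − 1)·CV²)). At CV 1.0 this is sqrt(1 + 14/13) = 1.44; at CV 0.6 it is sqrt(1 + 14/(13 × 0.36)) = 2.00. It differs from the population mean by r/CV standard deviations: at r = 0.3, that is 0.6 SD at CV 0.5 and 0.3 SD at CV 1.0. The CVs are assumed.

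**Step 4: the remedy.** In the least-squares setting of Step 1, the unadjusted mean covers about 95% at every R², and adding b²·s²(x)/n to the variance gives about 96%.

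**The case against.** Several points on the other side stand.

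- A shortfall needs a non-zero slope, and the documents report none for Lp(a). A reader might infer that the SE is certain to be too small; it is not. A reader might also take the proof-of-concept LDL-C results (Protocol 1 and 3.3: 49.2% mean reduction in 9 patients, 37.3% in the 3 null/null patients) as evidence of a material R². They concern LDL-C rather than Lp(a), and genotype rather than baseline, in 9 patients. The larger trial described there found similar lowering in null patients.
- A reader might infer that the plan will report the value at Lp(a) = 0. SAP 5.7.2.2 asks for means, so that is only one possible programming of an unstated detail. It is also an alternative to the narrow-SE problem, not an addition: its SE is wider, and the fault would be a different quantity.
- SAP 5.7.3 also plans an imputed Lp(a) mean with SE, and observed means and SDs, so a reader could form SD/√n. Only the 95% CI is unique to SAP 5.7.2.2. The SAP 5.7.3 entry points to the section for the other lipids, so it does not settle the evaluation point.
- The MMRM output is openly labelled as baseline adjusted, and conditional SEs are conventional. Baseline also supports the missing-at-random assumption that this sensitivity analysis relies on. These are good reasons to keep the covariate, but not to compare its SE directly with the primary one. For the on-treatment version, definition D is the least-squares mean itself, so there the issue is comparability only.

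It could also be argued that definition A makes the treated patients themselves the population. That does not rescue the conditional SE: with a fixed, fully observed group there would be no sampling error to report, and the primary PROC MEANS SE already treats patients as a sample.

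**Conclusion.** The point holds in a limited form and is minor. If the Lp(a) mean is taken at the sample-mean baseline, its SE and 95% CI are conditional on the observed baselines. They are too small for the population mean by sqrt(1 − R²) whenever percent change depends on baseline. At n = 14 and an assumed R² of 0 to 0.3, that is 0% to 16%, with coverage of about 95% down to 91% in a complete-data regression. The actual R² is unknown. The missing evaluation point is a gap in the specification whatever R² turns out to be.

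A reader might infer that the main LDL-C result is affected. It is not: the primary analysis, the secondary lipids analysed by the pattern-mixture approach and the binary endpoint use no baseline-adjusted mean, and no test or decision rule depends on these SEs.

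**What to change.** **Lp(a), SAP 5.7.2.2 and Protocol 11.4.3.2 (II).** Choose one:
- Fit the M-estimator to percent change with an intercept only.
- Keep baseline, centre it at its sample mean, report the intercept, and add slope² × s²(baseline)/n to each within-imputation variance before MIANALYZE.

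The second keeps the protocol's covariate, so only the SAP needs a sentence. The first departs from the protocol text and should be recorded in SAP 1.2.4 or in an amendment.

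**MMRM, SAP 5.7.1.1 and Protocol 11.4.3.1.** Keep the baseline covariate. Report the week-24 least-squares mean with the marginal SE, using the same added term, so that it can be compared with the primary PROC MEANS SE. Dropping the covariate would weaken the missing-at-random analysis and put the SAP at odds with the protocol.

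**Cost.** A sentence or two in the SAP, a few lines of code and slightly larger SEs. No new data are needed, and the primary result does not change.

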5.7.2.3. Binary Endpoint Variables

Binary secondary efficacy endpoints defined in Section 4.7.2 will be descriptively summarized using the ITT estimand for all patients in the ITT population with the proportion and 95% CI. Missing data will be imputed using the same PMM approach as described for the primary efficacy endpoint.

5.7.3. Summary of Results by Time Point

For Part B, central laboratory values (in conventional (US) and international units), percent change from baseline, and/or when appropriate absolute change from baseline (in conventional and international units) will be summarized at protocol scheduled visits by total patients for calculated LDL-C, Total-C, non-HDL-C, Apo B, and Lp(a). The time profile of each parameter will be plotted with the corresponding standard errors. Further details are described below:

- For lipids other than Lp(a): observed and imputed values, change from baseline (as applicable), and percent change from baseline, will be summarized using the same ITT estimand and PMM approach for missing data for all patients in the ITT population as described for endpoints above by mean and SE at all planned time points (see Section 5.7.2.1).
- For Lp(a): observed and imputed values, and percent change from baseline, will be summarized using the same ITT estimand and multiple imputation approach for missing data for all patients in the ITT population as described above by mean and SE at all planned time points (see Section 5.7.2.1).
- Observed data raw values, change from baseline (as applicable), and percent change from baseline response variables will be descriptively summarized using the ITT estimand for all patients in the ITT population by patient counts, mean, SD, median, Q1, Q3, minimum, and maximum at all planned time points.
- Observed data raw values, change from baseline (as applicable), and percent change from baseline response variables will be descriptively summarized using the on-treatment estimand for all patients in the mITT population by patient counts, mean, SD, median, Q1, Q3, minimum, and maximum at all planned time points. On-treatment estimand is defined as all secondary efficacy endpoints values collected during the efficacy treatment period (Section 3.1.2).

5.7.4. Analysis of Efficacy Variables for Part A and Part C

For Part A treatment and observation period, observed central laboratory values (in conventional (US) and international units), percent change from baseline, and/or when appropriate absolute change from baseline (in conventional and international units) will be descriptively summarized

at protocol scheduled visits by total patients in the safety analysis set within Part A for calculated LDL-C, Total-C, non-HDL-C, Apo B, and Lp(a). Descriptive statistics include patient counts, mean, SD, median, Q1, Q3, minimum, and maximum.

For Part C treatment period, similar analyses will be performed for all patients in the Part C safety analysis set and by main study part (Part A or Part B) in which patients are originally enrolled at the beginning of the study. The time profile of each parameter may be plotted with the corresponding standard errors.

5.7.5. Pooled Analysis of Efficacy Variables

Lipids analyses will also be performed on the pooled data in the pooled safety analysis set by patient groups. Observed central laboratory values (in conventional (US) and international units), percent change from baseline, and/or when appropriate absolute change from baseline (in conventional and international units) will be descriptively summarized over time by patient groups for calculated LDL-C, Total-C, non-HDL-C, Apo B, and Lp(a). Descriptive statistics include patient counts, mean, SD, median, Q1, Q3, minimum, and maximum.

5.8. Analysis of Safety Data

In general, for main study part (Part A or Part B), the summary of safety results for patients in the safety analysis set will be presented by each study part. No formal inferential testing will be performed. Summaries will be descriptive in nature.

For Part C, the summary of safety results for patients in the Part C safety analysis set will be presented for all patients and by main study part (Part A or Part B) in which patients are originally enrolled at the beginning of the study.

In addition, the safety analyses will be performed on the pooled data in the pooled safety analysis set. The summary of safety results will be presented by patient groups defined in Section 2.4.1.

General common rules

All safety analyses will be performed, unless otherwise specified, using the following common rules:

- Safety data in patients who do not belong to the safety analysis set (i.e., exposed but not enrolled) will be listed separately.
- PCSV values are defined as abnormal values considered medically important by the Sponsor according to predefined criteria/thresholds based on literature review and defined by the Sponsor for clinical laboratory tests and vital signs (PCSV version dated January 2009 [[Appendix 10.4](#)]). Considering that the threshold defined in the PCSV list for monocytes and basophils can be below the ULN, the following PCSV criterion will be used for the PCSV analysis of monocytes and basophils:
 - PCSV criterion for monocytes: >0.7 Giga/L or $>ULN$ (if $ULN \geq 0.7$ Giga/L).
 - PCSV criterion for basophils: >0.1 Giga/L or $>ULN$ (if $ULN \geq 0.1$ Giga/L).

- PCSV criteria will determine which patients had at least 1 PCSV during the respective TEAE periods, taking into account all evaluations including unscheduled or repeated evaluations.
- The treatment-emergent PCSV denominator for a given parameter will be based on the number of patients assessed for that given parameter at least once during the respective TEAE periods.
- All measurements, scheduled or unscheduled, fasting or not fasting, will be assigned to Global Analysis Windows defined in [Appendix 10.2](#) in order to provide an assessment for the screening visit through follow-up visit time points.
- For quantitative safety parameters including central laboratory measurements and vital sign scores, descriptive statistics will be used to summarize observed values and change from baseline values by visit.

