4.8.2. Laboratory Safety Variables

Clinical laboratory tests will consist of blood analyses (including hematology, clinical chemistry and other) and urinalysis. Clinical laboratory values will be converted and analyzed in both international units and US conventional units, with associated normal ranges provided by the

central laboratory. Both actual test values and “change from baseline” values (defined as the post-baseline value minus the baseline value) will be used in the result summaries. Potentially clinically significant values (PCSV) ranges will be applied to the laboratory test values as applicable (see [Appendix 10.4](#) for PCSV definitions). For those laboratory tests that do not have PCSV ranges, central laboratory normal ranges will be applied to identify out-of-range values. All laboratory test samples will be collected before study treatment administration during the protocol scheduled visits.

Unless otherwise specified below, blood samples for clinical laboratories will be collected at the protocol scheduled visits. The laboratory parameters (excluding those considered as efficacy parameters) will be classified as follows:

Hematology:

- Red blood cells and platelets: hemoglobin, hematocrit, erythrocytes count, platelets count, red blood indices
- White blood cells: white blood cells, neutrophils, lymphocytes, monocytes, basophils, eosinophils

Clinical chemistry:

- Metabolism: glucose, total protein, albumin, creatine phosphokinase
- Electrolytes: sodium, potassium, chloride, calcium, bicarbonate
- Renal function: creatinine, blood urea nitrogen (BUN), uric acid
- Liver function: Alanine aminotransferase (ALT), aspartate aminotransferases (AST), alkaline phosphatase (ALP), total bilirubin, LDH

Non-Efficacy Lipid Panel

HDL-C, TG, Apo A-1, Apo CIII, Apo E, and ratio Apo B/Apo A-1.

Urinalysis

Urinalysis will include the following parameters: color, clarity, pH, specific gravity, ketones, protein, glucose, blood, bilirubin, leukocyte esterase, nitrite, WBC, RBC, hyaline and other casts, bacteria, epithelial cells, crystals, and yeast.

Other

TSH, sex hormones (luteinizing hormone, follicle stimulating hormone, estradiol, and total testosterone).

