6.3. Data Handling Convention for Missing Data

Missing data will not be imputed in listings. This section includes the methods for missing data imputation for some summary analyses, if necessary.

Date and Time of First/Last Study Treatment

Since the study drug is administered at the site, the date and time of study drug administration are filled in e-CRF. No missing data is expected. Date of first/last administration is the first/last start date of study drug provided in e-CRF.

Adverse Event

If the intensity of a TEAE is missing, it will be classified as “severe” in the frequency tables by intensity of TEAEs. If the assessment of relationship of a TEAE to the investigational product is missing, it will be classified as related to the investigational product.

When the partial AE date/time information does not indicate that the AE started prior to study treatment or after the TEAE period, the AE will be classified as treatment-emergent.

Medication/Procedure

No imputation of medication/procedure start/end dates or times will be performed. If a medication date or time is missing or partially missing and it cannot be determined whether it was taken prior or concomitantly or stopped prior to the first study treatment administration, it will be considered as concomitant medication/procedure.

Potentially Clinically Significant Value (PCSV)

If a patient has a missing baseline value, this patient will be grouped in the category “normal/missing at baseline.”

For PCSVs with 2 conditions, one based on a change from baseline value and the other on a threshold value or a normal range, with the first condition being missing, the PCSV will be based only on the second condition.

For a PCSV defined on a threshold and/or a normal range, this PCSV will be derived using this threshold if the normal range is missing; e.g., for eosinophils the PCSV is >0.5 giga/L or $>ULN$ if $ULN \geq 0.5$ giga/L. When ULN is missing, the value 0.5 should be used.

Measurements flagged as invalid by the laboratory will not be summarized or taken into account in the computation of PCSVs.

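### The special PCSV rule for monocytes and basophils in SAP 5.8 is joined by 'or', so read literally it never moves the cut-off and does not do what it was written for

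*SAP*

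**What the plan says.** The general rules in SAP 5.8 define the concept first: "PCSV values are defined as abnormal values considered medically important by the Sponsor". They then give the reason for an exception: "Considering that the threshold defined in the PCSV list for monocytes and basophils can be below the ULN". Two criteria follow.

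- Monocytes: "PCSV criterion for monocytes: >0.7 Giga/L or" above ULN, the second part applying if ULN is at least 0.7 Giga/L.
- Basophils: "PCSV criterion for basophils: >0.1 Giga/L or" above ULN, the second part applying if ULN is at least 0.1 Giga/L.

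Three other places bear on the same rule.

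- **SAP 6.3** covers PCSVs defined on a threshold and/or a normal range: "this PCSV will be derived using this threshold if the normal range is missing". Its worked example is eosinophils, with a 0.5 Giga/L criterion of the same 'or' form: "When ULN is missing, the value 0.5 should be used".
- **Appendix 10.4**, which SAP 4.8.2 and 5.8.3 cite for the PCSV definitions, lists monocytes as above 0.7 Giga/L with no ULN clause. It has no basophil row. Its eosinophil row carries the 'or ULN' wording.
- **SAP 4.8.2** says laboratory values come "with associated normal ranges provided by the" central laboratory. Neither document prints a ULN for any of these cells.

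**The concern.** The exception is there to deal with a fixed threshold that sits inside the normal range. A rule for that purpose has to raise the cut-off to ULN in those cases. Joining the two conditions with 'or' can only widen the set of flagged values, never narrow it. A within-range count would then be tabulated as abnormal and medically important, against the section's own definition.

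The outputs at stake are the PCSV incidence tables and listings. Under SAP 5.8 a patient counts once any evaluation in the TEAE period meets the criterion, including unscheduled and repeat ones. SAP 5.8.3 repeats the table by baseline category and judges a normal baseline by the same criterion. A child whose within-range baseline is above the threshold would therefore also be placed in the abnormal-baseline category. Part B plans 14 children (Protocol 11.2) and has no control arm, so one child is about 7 percentage points (1/14) and no comparator shows a background flag rate.

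**Working it through.** **Step 1: the rule as logic.** Let T be the fixed threshold (0.7 for monocytes, 0.1 for basophils, in Giga/L) and x the measured value.

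- Literal rule: flag if x > T, or if (ULN ≥ T and x > ULN).
- If ULN ≥ T, then x > ULN implies x > T. The second condition lies inside the first, and the rule is x > T.
- If ULN < T, the second condition is switched off, and the rule is again x > T.

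The literal rule equals x > T in every case.

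**Step 2: grid check.** ULN ran from 0.01 to 2.00 and x from 0 to 3.00 in steps of 0.01, which gives 200 × 301 = 60,200 pairs per parameter. The alternative reading takes ULN as the cut-off if ULN ≥ T, and T otherwise.

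| Parameter | T | Pairs where literal rule differs from x > T | Pairs flagged with x ≤ ULN, literal | Same, alternative reading |
|---|---|---|---|---|
| Monocytes | 0.7 | 0 | 8,515 | 0 |
| Basophils | 0.1 | 0 | 18,145 | 0 |
| Eosinophils | 0.5 | 0 | 11,325 | 0 |

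The pair counts confirm the identity; they are not event rates. Example with an assumed monocyte ULN of 0.9: a value of 0.8 is within range and is flagged by the literal rule, but not by the alternative.

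**Step 3: the places side by side.** SAP 5.8 gives the purpose. SAP 6.3 falls back on the fixed threshold when the normal range is missing, which makes sense only if ULN governs when it is present. Appendix 10.4 shows the monocyte threshold alone and has nothing for basophils. Under SAP 5.8.3 a parameter without a PCSV criterion may be tabulated against the normal range, so someone working from 10.4 alone could treat basophils differently from someone working from 5.8.

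**Step 4: illustrative size for monocytes.** Assumptions, none from the documents: log-normal values, the 97.5th percentile at ULN, a median of 0.45 to 0.50, and independent samples.

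- s = ln(ULN/median)/1.96 and p = 1 − Φ(ln(0.7/median)/s).
- ULN 0.9, median 0.45: s = 0.3536, z = 0.4418/0.3536 = 1.249, p = 10.6%.
- ULN 0.9, median 0.50: s = 0.2999, z = 0.3365/0.2999 = 1.122, p = 13.1%.
- Above ULN, by construction: 2.5%.

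Number of scheduled Part B samples: the Part B schedule has post-baseline haematology at weeks 8, 12, 16 and 24. SAP 4.8.1 ends the Part B TEAE period the day before the first Part C dose. Footnote 15 of the protocol's Part C schedule puts Part C visit 1 on the day of Part B visit 11 (week 24). For a child who starts Part C then, the week-24 sample falls outside the Part B period and three remain.

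Chance of at least one flag in three samples, 1 − (1 − p)³:

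- ULN 0.9, literal rule: 28.5% (median 0.45) to 34.4% (median 0.50).
- ULN 0.9, cut-off at ULN: 1 − 0.975³ = 7.3%.
- ULN 0.8, literal rule: p = 6.6% to 8.0%, giving 18.6% to 22.2%.
- ULN at or below 0.7: no difference between the readings.

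**The case against.** The strongest reply is that the intent can be recovered. The purpose is stated, the ULN condition would be idle under a literal reading, and SAP 6.3 makes sense only if ULN normally governs. A careful programmer could well implement the intended rule. That stands: this is a drafting defect that could be programmed either way, not proof that the tables will be wrong. It does not remove the point, because the criterion as written contradicts its own stated reason.

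A second reply is that 5.8 expressly replaces the list threshold for these two cells, so the monocyte row in 10.4 is only the base value and the basophil criterion is supplied elsewhere. This is fair as to precedence. But 4.8.2 and 5.8.3 send the reader to 10.4 for the definitions, so it should carry the operative rule.

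Three stronger readings are tempting and not supported.

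- A reader might infer that the exception was also meant for eosinophils. The purpose sentence names only monocytes and basophils. Eosinophils share the wording through 6.3 and 10.4, and their purpose is an inference.
- A reader might take four Part B samples per child and treat the result as an upper bound. The count is three for children who start Part C at week 24. Unscheduled samples count for everyone, and follow-up visits at weeks 36 and 44 add samples for children who stay out of Part C, so four is neither the right count nor a bound.
- A reader might infer that over-flagging could hide a safety signal. Nothing in the documents shows how. SAP 5.8.3 also summarises actual values and changes from baseline by visit and lists the flagged measurements, and Protocol 10.1.1 has the investigator judge clinical significance separately.

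**Conclusion.** The point holds for monocytes and basophils, and the logic is exact: the criterion in SAP 5.8 has no effect as written and flags within-range values whenever the laboratory ULN exceeds the threshold. SAP 5.8 itself says this can happen. For eosinophils only the shared wording is established.

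The importance is low. The effect is confined to descriptive PCSV counts, the baseline-category split and listings for a few differential counts; no efficacy analysis uses them. The size cannot be fixed from the documents because no ULN is given. Under the stated assumptions with ULN 0.9, about 11-13% of samples from a normal population are flagged against 2.5%. For children who start Part C at week 24, about 28-34% have at least one Part B flag from scheduled samples, against about 7%. Correlation between a child's samples would lower these per-child figures; unscheduled samples, follow-up visits and Part C would add to the count. No size was worked out for basophils or eosinophils.

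**What to change.** In SAP 5.8 and Appendix 10.4, state the criterion for monocytes (T = 0.7 Giga/L) and basophils (T = 0.1 Giga/L) as: *above ULN if ULN ≥ T; above T if ULN < T or ULN is missing*. Add the basophil row to 10.4. Put the eosinophil criterion (T = 0.5 Giga/L) in 10.4 and 6.3 into the same form, or state that the plain threshold is intended there.

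The cost is a wording change in the SAP before database lock. No data collection, design element or clinical rule changes.
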